### 2.2 Objectives

The primary objectives of the study are:

- to determine the effect of a delayed intake of 6 hours or of a missed pill on cervical mucus score compared to cervical mucus score during reported perfect daily use of norgestrel 75 mcg
- to estimate the duration of the protective effect of cervical mucus after last pill intake of norgestrel 75 mcg during reported perfect use (The protective effect of cervical mucus is considered as present when the score is below or equal 4.)

---

 defined as the day before the delayed intake or the missed pill

The secondary objectives of the study are:

[figure not shown]
- to evaluate and compare the percentage of subjects with a protective cervical mucus score during reported perfect daily use of norgestrel 75 mcg, during a treatment period with a delayed intake of 6 hours and during a treatment period with a missed pill of norgestrel 75 mcg.
- to evaluate and compare the ovarian activity during reported perfect daily use, during a treatment period with a delayed intake of 6 hours and during a treatment period with a missed pill of norgestrel 75 mcg.
- to assess if a combination of cervical mucus score and ovarian status can be considered as a measure of protection from conception during reported perfect daily use, during a treatment period with a delayed intake of 6 hours and during a treatment period with a missed pill of norgestrel 75 mcg.
- to determine levonorgestrel pharmacokinetics after a single dose of norgestrel 75 mcg, at steady state, after a delayed intake and after a missed pill.
- to assess the safety of norgestrel 75 mcg taken daily for 12 weeks.

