## 2.5 Sample Size Consideration

Approximately 70 subjects will be screened to have at least 45 subjects who complete the study.

The primary analysis is based on the score of cervical mucus as a quantitative variable because it is expected to be the most powerful analysis based on the consistent mechanism of action of norgestrel on cervical mucus. However the justification of the sample size will not be based on the primary analysis as there is no basis provided by published data on this parameter, such as order of magnitude of the variance covariance matrix of the change from time point of reference. This is the reason why the sample size calculation will be based on proportions of women with no loss of protection.

A total sample size of 45 subjects who complete the study should allow to detect a loss of protection that would demonstrate a pertinent effect on a substantial proportion of the population. Indeed if the difference between a cycle (or day) with a perfect use and a cycle (or day) with an infringement in the schedule is 14 % in the expected proportions of women with a loss of protection at any time and if the proportion of discordances between the 2 situations is 17% then the exact power is equal to 79.1%. If the expected difference in proportions is 15% with a rate of discordance of 18% then the exact power is 82.4% for an unconditional test. The expected difference in proportions need, therefore, to reach 14-15 % to get a sufficient power for detecting a significant difference. This difference in proportions is a substantial difference knowing that most of change in status are in the same direction i.e. from protection to loss of protection.

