## 3.0 STATISTICAL METHODS

### 3.1 Statistical Handling Policy and Analysis Conventions

This section details general policies to be used for the statistical analyses. Departures from these general policies may be given in the specific detailed sections of this SAP. When this situation occurs, the rules set forth in the specific section take precedence over the general policies. The following policies will be applied to all data presentations and analyses.

- All statistical tests will use a significance level of  $\alpha = 0.05$ . Two-tailed tests will be performed for all analyses that use statistical testing.
- All p-values will be rounded to 3 decimal places. All p-values that round to 0.000 will be presented as '<0.001' and p-values that round to 1.000 will be presented as '>0.999'. Any

p-value  $\leq 0.05$  will be considered statistically significant and will be marked with one asterisk (e.g., 0.025\*).

- Summary statistics will consist of the number and percentage of responses in each category for discrete variables, and the mean, median, standard deviation (SD), minimum, and maximum for continuous variables.
- All mean values will be formatted to one more decimal place than the measured value. Standard deviation values will be formatted to two more decimal places than the measured value. Median values will be formatted to same decimal place as the measured values when that is possible without losing accuracy; otherwise, they will be formatted to one more decimal place than the measured values.
- All percentages will be rounded to one decimal place. The number and percentage of responses will be presented in the form XX (XX.X), where the percentage is in the parentheses. The denominator for percentage calculations will be the number of non-missing observations.
- All listings will be sorted for presentation in order of site number, subject number, and date of procedure or event.
- All analysis and summary tables will have the population sample size (n and % (% will not be shown in the column header if the table also presents means)) for each treatment group in the column heading.
- Calculating change from baseline to a visit will be done as follows: Change = Visit – Baseline.
- Baseline is defined as the last data point before the day of infringement (i.e. V2R-1 or V3R-1).
- Version 9.4 of SAS® or higher will be the statistical software package used to produce all summaries, listings, statistical analyses, and graphs.

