### 3.7.2 Secondary Efficacy Analyses

#### 3.7.2.1 Cervical mucus protection in each type of treatment period

The aim of this secondary objective is to assess the level of cervical mucus protection during reported perfect use, during a treatment period with a delayed pill intake of 6 hours and during a treatment period with a missed pill of norgestrel 75 mcg. The FASM population will be used for the analysis and a sensitivity analysis will be done using ITT and PP.

The time frames are:

- reported perfect use: all the visits of the period 1
- delayed pill intake: all the visits of the period 2 for Arm A and all the visits of period 3 for Arm B.
- missed pill: all the visits of the period 2 for Arm B and all the visits of period 3 for Arm A.

The assessment criterion is the cervical mucus score. The cut off is a cervical mucus score of 4. There is conception protection by cervical mucus if the cervical mucus score is  $\leq 4$ .

The endpoints are:

- The percentage of subjects with cervical mucus score  $\leq 4$ , between 5 and 8, and  $\geq 9$  in reported perfect use period
- The percentage of subjects with cervical mucus score  $\leq 4$ , between 5 and 8, and  $\geq 9$  in delayed pill intake periods
- The percentage of subjects with cervical mucus score  $\leq 4$ , between 5 and 8, and  $\geq 9$  in missed pill periods
- The percentage of subjects with cervical mucus score  $\leq 4$  in all periods

If the cervical mucus was too thick to be collected (and thus a cervical mucus score could not be obtained) the analysis will consider the sample to have good contraception protection and have a cervical mucus score  $\leq 4$ . Otherwise if the cervical mucus score is missing the subject will not be included in the analysis. A period must have at least 7 cervical mucus assessment to be included in the summaries. A stratified McNemar test (stratification on the site, CMH option in SAS) will be used to compare the distribution of cervical mucus scores in the perfect use period to the delayed and missed pill periods (pairwise vs perfect use).

The worst (meaning highest) cervical mucus score in the period will be used for the analyses.

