### 3.7.2.2 Ovarian activity in each type of treatment period

The aim of this secondary objective is to describe the distribution of the ovarian status among the subjects, during reported perfect use, during a treatment period with a delayed pill intake of 6 hours and during a treatment period with a missed pill of norgestrel 75 mcg. The adjudication committee will evaluate whether cycles should be excluded from analyses (including period 1 cycles if low compliance of taking study drug). The details for the review process will be defined in a separate document prepared for the adjudication process. The FASO population will be used for the analysis and a sensitivity analysis will be done using ITT and PP.

The time frames are:

- reported perfect use period: all the visits of the period 1
- delayed pill intake period: all the visits of the period 2 for Arm A and all the visits of period 3 for Arm B
- missed pill period: all the visits of the period 2 for Arm B and all the visits of period 3 for Arm A

The assessment criterion is the OS as defined in Appendix 5.4.

The OS are ranked depending on the risk of conception:  $OS_{nlp} > OS_{alp} > OS_a > OS_q$ . The OS classification will be determined by the adjudication committee.

For each treatment period the most risky OS will be considered.

The endpoints are:

- The percentage of subjects with  $OS_q$ ,  $OS_a$ ,  $OS_a/OS_{alp}$  and  $OS_{nlp}$  in reported perfect use period
- The percentage of subjects with  $OS_q$ ,  $OS_a$ ,  $OS_a/OS_{alp}$  and  $OS_{nlp}$  in delayed pill intake periods
- The percentage of subjects with  $OS_q$ ,  $OS_a$ ,  $OS_a/OS_{alp}$  and  $OS_{nlp}$  in missed pill periods
- The percentage of subjects with  $OS_{nlp}$  in all periods

A stratified McNemar test (stratification on the site, CMH option in SAS) will be used to compare the distribution of ovarian activity classification in the perfect use period to the delayed and missed pill periods (pairwise vs perfect use). The worst (meaning most risk of ovulation) ovarian activity category in the period will be used for the analyses.

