		Visits twice a week if follicle < 15 mm  Visits every other day for a maximum of 6 days if a growing follicle ≥ 15 mm identified upon TVUS(b)	Visits twice a week if follicle < 15 mm  Visits every other day for a maximum of 6 days if a growing follicle ≥ 15 mm identified upon TVUS(b)	Delayed/missed pill period Three consecutive days		Visits twice a week if follicle < 15 mm  Visits every other day for a maximum of 6 days if a growing follicle ≥ 15 mm identified upon TVUS(b)		Delayed/missed pill period Three consecutive days			Visits every other day for a maximum of 12 days if a growing follicle ≥ 15 mm identified upon TVUS(c)			
				V2 0+1	V2 0A	V2 0B	V2 0+1		V3 0+1	V3 0A	V3 0B	V3 0+1		
Study medication intake		X	X	X(i)	X(j)		X(k)	X	X(i)		X(j)	X(k)		
Diary completion		X	X	X	X	X	X	X	X	X	X	X	X	X
TVUS	X	X	X	X	X	X	X	X	X	X	X	X	X	X(l)
Mucus analysis		X(m)	X	X(n)	X(o)	X(p)	X(q)	X	X(n)	X(p)	X(o)	X(q)	X	
PK samples		X(r)(s)	X(t)	X(u)	X(v)	X(w)	X(x)	X(t)	X(u)	X(w)	X(v)	X(x)	X	
P4	X	X	X	X	X	X	X	X	X	X	X	X	X	X
E2, FSH, LH		X	X	X			X	X	X			X	X	X(y)
Prior and concomitant treatments	X	X	X	X	X	X	X	X	X	X	X	X	X	X
Adverse events and bleeding patterns	X	X	X	X	X	X	X	X	X	X	X	X	X	X

- (a) Only if follicle ≥ 15 mm is observed after Day 73 AND the criteria for stopping the extra-visits were not fulfilled by Day 84
- (b) Extra visits will be stopped before 6 days if there is no postovulatory image after 6 days
- (c) Extra visits will be stopped before 12 days if there is no postovulatory image after 6 days or if the P4 levels are > 30 nmol/L at 1 visit or > 10 nmol/L at 2 consecutive visits.
- (d) Randomization at 1st visit of treatment period 2
- (e) Vital signs include heart rate, systolic and diastolic blood pressure after at least 2-minute rest and height and weight (at screening only).
- (f) Pap smear to be performed according to current US guideline if an abnormal cervical lesion is detected during the gynecological examination
- (g) At V11 only, before first pill intake
- (h) At V11, last visit of treatment period 1 and last visit of treatment period 2
- (i) Study pill intake will be at 9 am ± 1 hour and will be noted as T2/3R-1 (actual treatment time at Day 41 or Day 69)
- (j) Study pill intake at T2/3R-1+ 6h ± 15 min
- (k) Study pill intake at T2/3R-1 ± 30 min
- (l) TVUS up to observation of postovulatory image

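### The secondary whole-period mucus and ovarian tests compare only with period 1, so they cannot separate infringement from time on treatment, and the order-balanced delayed-versus-missed test is not planned for these endpoints

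*SAP*

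**What the plan says.** Among the secondary objectives in SAP section 2.2 is "to evaluate and compare the ovarian activity during reported perfect daily use", during a delayed-pill period and during a missed-pill period. The mucus objective has the same three-way form.

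Sections 2.4.2, 3.7.2.1 and 3.7.2.2 define perfect use as all visits of period 1. Each endpoint takes the worst value of the period. The tests are stratified McNemar tests:

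- Mucus (3.7.2.1): "compare the distribution of cervical mucus scores in the perfect use period to the delayed and missed pill periods (pairwise vs perfect use").
- Ovarian status (3.7.2.2): "compare the distribution of ovarian activity classification in the perfect use period to the delayed and missed pill periods (pairwise vs perfect use").

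The endpoint table in section 2.4.2 lists McNemar for these endpoints and names no pair. Under section 2.3 and footnote (d) of section 5.1, women are randomised at the first visit of period 2. One arm has the delayed pill in period 2 and the missed pill in period 3; the other arm has the reverse.

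Delayed versus missed appears in two places, both in section 3.7.1 and both for mucus in the three-day windows. One is a contrast of the primary mixed model, which includes period and sequence and is coded in the SAS example. The other is a stratified McNemar test under the subordinate primary objective.

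**The concern.** Three conditions are to be compared, and the design protects one pair. Delayed and missed each occur in period 2 for one arm and in period 3 for the other, so a shift common to both arms cancels. Perfect use has no such balance. It is always the first 28 days on drug, directly after a screening period in which ovulatory status was shown. The planned secondary tests use only the unprotected pairs.

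If ovarian activity or mucus settles further after the first cycle, a harmful infringement can look neutral against period 1. If it drifts the other way, a harmless infringement can look harmful. Section 3.1 has every p-value of 0.05 or less flagged as significant, so a drift could be reported as an effect of the delayed or missed pill. For ovarian status no other test in the SAP could correct that impression.

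**Working it through.** **1. Which tests rest on which comparator**

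| Endpoint | Comparator | Delayed vs missed planned? |
|---|---|---|
| Mucus change, primary model (3.7.1) | day before infringement, same period | yes, model contrast |
| Mucus protection, subordinate primary (3.7.1) | day before infringement, same period | yes, McNemar |
| Worst mucus score of the period (3.7.2.1) | period 1 | no |
| Worst ovarian status of the period (3.7.2.2) | period 1 | no |

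**2. What each comparison estimates**

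Let p1, p2, p3 be the at-risk proportions under unbroken use in periods 1, 2 and 3. Let d and m be the amounts that a delayed and a missed pill add. With equal arms and no carryover:

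- Delayed vs period 1: d + (p2 + p3)/2 − p1
- Missed vs period 1: m + (p2 + p3)/2 − p1
- Delayed vs missed: [(p2 + d) − (p3 + m) + (p3 + d) − (p2 + m)]/2 = d − m

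The first two carry the full drift; the third carries none. With arms of 23 and 22, a remainder of (p2 − p3)/45 is left in the third: for p2 = 20% and p3 = 30%, −10/45 = −0.2 points.

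Example of masking (assumed rates): p1 = 30%, p2 = p3 = 20%, m = 10 points. Missed vs period 1 is 10 + 20 − 30 = 0.

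**3. The plan's own figures**

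Section 2.5 rests on 45 completers and a perfect-use versus infringement difference that "is 14 % in the expected proportions of women with a loss of protection at any time", with 17% discordant pairs and power 79.1%; alternatively 15%, 18% and 82.4%. With p10 = (0.17 + 0.14)/2 = 0.155 and p01 = (0.17 − 0.14)/2 = 0.015, full enumeration for an unconditional exact McNemar test gives 79.10% at one-sided 0.05. The second scenario (0.165 and 0.015) gives 82.43%. Both stated figures reproduce. Section 3.1, however, says "Two-tailed tests will be performed for all analyses that use statistical testing"; at two-sided 0.05 the same test gives 69.5% and 73.6%. That mismatch is a separate matter. What counts here is that a difference of 14-15 points is the size the trial is meant to detect, so a drift of 10-15 points is of similar size.

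**4. False-positive rate with no infringement effect**

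Inputs from the SAP: n = 45 (section 2.5) and two-sided 0.05 (section 3.1). Assumptions: arms of 23 and 22; three correlated binary outcomes per woman from a latent normal variable with correlation 0.5 or 0.8; asymptotic McNemar without site strata; 20,000 runs. All at-risk rates are assumed. Ranges cover both correlations and, against period 1, both infringement types.

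| At risk in periods 1/2/3 | Each test vs period 1 rejects | Delayed vs missed rejects |
|---|---|---|
| 10/10/10% | 4.0-4.8% | 4.4-4.7% |
| 5/10/15% | 27-36% | 4.2-4.6% |
| 10/20/20% | 31-45% | 4.4-4.8% |
| 10/20/30% | 55-74% | 3.9-4.2% |
| 5/20/20% | 69-84% | 4.2-4.6% |

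With the exact conditional McNemar test the pattern is the same at lower rates: for 10/20/20%, 21-26% against period 1 and about 1.5-2.2% for delayed versus missed.

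**5. Two features specific to the mucus endpoint**

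The first mucus sample of period 1 is taken before the first pill (section 5.1, footnote m), and the endpoint is the highest score over all period 1 visits. A pre-drug score can thus become the perfect-use value. Conversely, periods 2 and 3 contain three consecutive infringement visits, so the highest score is taken over a different set of visits. The first feature can raise the period 1 value and the second can raise the later ones, so the net direction cannot be told.

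**The case against.** The SAP calls the study exploratory, and section 3.7.2.2 states its aim as describing the distribution of ovarian status. Percentages for all three conditions will be reported, so delayed and missed can be set side by side without a p-value. This lowers the weight of the point. It does not remove it, because section 2.2 asks for a comparison and both sections plan significance tests.

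Putting perfect use first is a feature of the design, and no SAP wording can undo it. Nor does delayed versus missed answer infringement versus perfect use: if both infringements do equal harm, it is null. Both statements stand, and for that reason the added test complements the period 1 tests and does not replace them. It also assumes no differential carryover, and periods 2 and 3 follow each other directly (D29-D56, D57-D84).

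A reader might infer that every test in the plan is confounded with time on treatment, or that the randomised comparison is missing altogether. The SAP supports neither reading. The primary and subordinate primary analyses compare with the day before infringement in the same period, and both include delayed versus missed for mucus.

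A reader might also want to use the pre-infringement visits of periods 2 and 3 (D29-D40, D57-D68) as a cleaner perfect-use reference. Twelve days at two visits a week give about three or four visits, while section 3.7.2.1 requires at least seven mucus assessments per period. The cycle days differ, and in period 3 those visits follow the period 2 infringement. I do not recommend it.

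**Conclusion.** The point holds for the secondary tests in sections 3.7.2.1 and 3.7.2.2. They cannot separate the effect of an infringement from that of time on treatment. For ovarian status the SAP plans no randomised comparison at all; for mucus the gap is confined to the worst score over the whole period.

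The confounding equals the average of the period 2 and period 3 rates under unbroken use minus the period 1 rate, point for point. The SAP gives neither the size nor the direction of that difference. The simulated rejection rates show what a drift would do, not that one occurs; without drift all the tests hold their level. Given the exploratory setting, this is a correction that should be made, not one that undermines the primary analysis.

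**What to change.** - In sections 3.7.2.1 and 3.7.2.2, add a within-woman comparison of the delayed-pill and missed-pill periods across both sequences, for worst mucus score and worst ovarian status. Use the stratified McNemar test already planned, with the same categories. If the sequences end unbalanced, use a period-adjusted paired analysis such as the Mainland-Gart test.
- Keep the comparisons with period 1 as supportive, and state that they are confounded with time on treatment.
- State that delayed versus missed assumes no differential carryover and cannot show whether both infringements are harmful or both harmless.
- Name the compared pairs in the endpoint table of section 2.4.2.

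The data are already collected. The cost is SAP wording, one more comparison per endpoint and a weaker claim for the tests against perfect use. The added test has limited power: if the differences and discordances of section 2.5 applied to it (an assumption), two-sided power with 45 women would be about 69.5-73.6%.

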### 3.7.2.3 Protection from conception based on cervical mucus score and OS (binary and ternary analyses)

Based on cervical mucus score and OS only, the aim of these exploratory analyses are to assess if a combination of cervical mucus score and ovarian status can be considered as a measure of protection from conception or not and the level of protection, during reported perfect use of norgestrel 75 mcg and after a delayed intake/missed pill. The FASC population will be used for the analysis and a sensitivity analysis will be done using ITT and PP.

[figure not shown]
For both analyses, the assessment criteria will be the OS and the highest cervical mucus score during the 3 visits before a postovulatory image is obtained including the visit when the postovulatory image is obtained.

For the OS, the risk of conception is ranked depending on the OS:  $OS_{nlp} > OS_{alp} > OS_a > OS_q$  and for each treatment period the most risky OS will be considered.

#### Binary analysis

The aims of this analysis is to determine whether a subject is protected or not, according to the algorithm presented below:

#### Conception protection based on OS and cervical mucus score (binary analysis)

The endpoints will be, for each treatment period, the distribution of subjects:

- considered as protected:  $OS_q$  or  $OS_a$  OR cervical mucus score  $\leq 4$
- considered as at risk of conception:  $OS_{alp}$  or  $OS_{nlp}$  AND cervical mucus score  $\geq 5$

#### Ternary Analysis

The aim of this analysis is to determine the level of protection for a subject, according to the table below.

#### Conception protection based on OS and cervical mucus score

		Ovarian Status			
		$OS_q$	$OS_a$	$OS_{alp}$	$OS_{nlp}$
Highest Mucus score	0-4	maximum	maximum	maximum	maximum
	5-8	maximum	maximum	medium	medium
	9-12	maximum	maximum	medium	minimum

The classification of OS (and thus conception protection level also) will be determined by the adjudication committee.

The endpoints will be, for each treatment period, the distribution of subjects with:

- Minimum protection or unlikely to be protected:  $OS_{nlp}$  and cervical mucus score  $\geq 9$
- Medium protection or likely to be protected:  $OS_{nlp}$  and cervical mucus score comprised between 5 and 8 or  $OS_{alp}$  and cervical mucus score  $\geq 5$
- Maximum protection or highly likely to be protected:  $OS_q$  or  $OS_a$  or a cervical mucus score  $\leq 4$

